## 8.3.1. Patient Baseline Characteristics

Baseline variables are collected at the index date. These variables reflect the patient's demographics and status at the initiation of filgotinib treatment including relevant medical history at or prior to the index date. Baseline variables will include (as per availability by each registry):

- Age (at baseline)
- Sex
- Body mass index (BMI)
- Long-time smoking (for >10 years (Kristensen et al., 2023) (either current or past smoking)
- Date of UC diagnosis

- Severity of UC (for details, see Annex 3 Table 5)
- Renal impairment (for details, see Annex 3 Table 5)
- Hepatic impairment
- Type and number of previous UC treatments prior to filgotinib initiation
- Date of filgotinib initiation
- Initial filgotinib dose
- Diagnosis of active TB at index date
  - Date of diagnosis
- Active serious infection at index date
  - Date of diagnosis
- Current pregnancy (at index date)
  - Start of pregnancy
- Age  $\geq 65$  (at index date)
- History of atherosclerotic CVD (angina, coronary heart disease, myocardial infarction, congestive heart failure, stroke, peripheral arterial disease)
- Other CV risk factors (diabetes mellitus, hypertension, obesity/BMI  $\geq$  30 kg/m^2)
- Current malignancy
- History of malignancy
- Concomitant use of other immunosuppressants
- Diagnosis of viral hepatitis
  - Date of diagnosis
- Diagnosis of herpes zoster
  - Date of diagnosis
- Screening for viral hepatitis
  - Date of screening
- Laboratory measurements (measurement within ±1 month of filgotinib index date, or any time during follow-up)
  - absolute neutrophil count (ANC)
  - absolute lymphocyte count (ALC)
  - hemoglobin (Hb)
- Use of live-attenuated vaccines
- History of VTE
- Recent surgery (i.e. surgery within 1 month (Singh et al., 2023) prior to the index date or at any time during follow-up; see also Annex 3 Table 5)
- Reduced mobility (for details, see Annex 3 Table 5)
- Recent hospitalization (hospitalization within 1 month prior to the index date or at any time during follow-up; see also Annex 3 Table 5)
- History of blood clotting disorders
- Concomitant use of combined hormonal contraceptives
- Concomitant use of hormone replacement therapy

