#### 8.4.2.4.1. Week 0 (Baseline)

Clinical data on demographics, date of diagnosis, IBD phenotype and phenotype history, location of previous IBD surgery, medical history, IBD medication history, and smoking status will be collected. Furthermore, the current clinical disease activity (Harvey-Bradshaw Index [HBI]/Simple Clinical Colitis Activity Index [SCCAI]), biochemical data (Hb, thrombocytes,

leucocytes, alanine aminotransferase [ALT], alkaline phosphatase, C-reactive protein [CRP], creatinine, fecal calprotectin), current IBD medication, and, if applicable, radiologic, and endoscopic information will be collected.

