#### 8.4.2.4.2. Follow-up Visits (Week 12, 24, 52, Year 2, 3, 4, 5, 6, 7, 8, 9, 10)

During follow-up visits, the following information is collected: current clinical disease activity (HBI/SCCAI), biochemical data (Hb, thrombocytes, leucocytes, ALT, alkaline phosphatase, CRP, creatinine, fecal calprotectin), current IBD medication, complications (surgery, hospitalization), AEs (events related to medication and infections), and, if applicable, radiologic and endoscopic information.

Details of variables to be collected in ICC can be found in Annex 3 – Table 5.

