## **Annex 3 Additional Information**

#### Variables of Interest

#### Table 5Variables of Interest and Their Availability by Registry

Variable	Availability in individual registries yes/no (additional comments)					
	ENEIDA (ES)	ICC (NL)	SWIBREG (SE)			
Variables assessed at baseline (start [index] date of filgotinib)						
Key patient characteristics						
Age: Date/year of birth	yes	yes	yes (Population Register)			
Sex	yes	yes	yes (Population Register)			
BMI	no (might be in medical report)	yes	yes (SWIBREG, but suboptimal coverage)			
Height	yes (not always available; might be in medical report)	yes	yes (SWIBREG, but suboptimal coverage)			
Weight	no (might be in medical report)	yes	yes (SWIBREG, but suboptimal coverage)			
Dx of UC	yes	yes	yes			
Date/year of Dx	yes	yes	yes			
Renal impairment (moderate to severe chronic kidney disease [stage 4 or 5])	yes (not always available; might be in medical report [and as described in the medical history of the patient])	yes (creatinine lab values are available)	yes (NPR via ICD10- and NCSP codes) (ICD10-codes: N17 - Acute renal failure N183 - Chronic kidney disease, stage 3 N184 - Chronic kidney disease, stage 4			

Variable	Availability in individual registries ves/no			
		(additional comments)		
	ENEIDA (ES)	ICC (NL)	SWIBREG (SE)	
	ENEIDA (ES)		SWIBREG (SE) N185 - Chronic kidney disease, stage 5 N189 - Chronic kidney disease, unspecified N19 - Unspecified kidney failure Y841- Kidney dialysis Z992 - Dependence on renal dialysis) NCSP-codes: DK001 - Installation of tunnelled hemodialysis catheter DK005 - Tunneled hemodialysis catheter replacement DR014 - Hemodiafiltration DR015 - Hemodialyis, acute DR016 - Hemodialyis, chronic DR020 - Continuous arteriovenous or venovenous hemofiltration DR025 - Preoperative hemodilution DR056 - Heparin-free dialysis DR060 - Home hemodialysis control DR061 - Home hemodialysis	
Severe hepatic impairment (Child Pugh C)	yes (not always available; might be in medical report)	yes	start yes (NPR via ICD-codes)	

Variable	Availability in individual registries yes/no (additional comments)			
	ENEIDA (ES)	ICC (NL)	SWIBREG (SE)	
UC treatment prior to initiation of filgotinib (specifically other JAKi's; advanced therapies; immunomodulators/immunosuppressants)	yes	yes	yes	
JAKi's	yes	yes	yes	
Advanced therapies – biologics (including TNFα inhibitors)	yes	yes	yes	
Advanced therapies – non-biologics	yes	yes	yes	

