Myocardial infarction	no (might be in medical report)	yes (as part of medical history/comorbidity)	yes (NPR)
Congestive heart failure	no (might be in medical report)	yes (as part of medical history/comorbidity)	yes (NPR)
Stroke	no (might be in medical report)	yes (as part of medical history/comorbidity)	yes (NPR)
Peripheral artery disease	no (might be in medical report)	yes (as part of medical history/comorbidity)	yes (NPR)
Other CV risk factors		yes (as part of medical history/comorbidity)	yes (NPR)
Diabetes mellitus (type 1 or 2)	yes (if not available, might be in medical report)	yes (as part of medical history/comorbidity)	yes (NPR)
Hypertension	yes (if not available, might be in medical report)	yes (as part of medical history/comorbidity)	yes (NPR)
Obesity/BMI	no (might be in medical report)	yes (as part of medical history/comorbidity)	yes (NPR)
Current malignancy	yes (if not available, might be in medical report)	yes (as part of medical history/comorbidity)	yes (Cancer Register)
Hx of malignancy	yes (if not available, might be in medical report)	yes (as part of medical history/comorbidity)	yes (Cancer Register)

Variable	Availability in individual registries yes/no (additional comments)		
	ENEIDA (ES)	ICC (NL)	SWIBREG (SE)
Previous VTE	yes (if not available, might be in medical report)	yes (as part of medical history/comorbidity)	yes (NPR)
Recent surgery (within 1 month prior to the index date or at any time during follow-up)	no (might be in medical report if related to IBD surgery)	yes (as part of medical history/comorbidity; history and location of IBD surgery is collected, and any IBD- surgery during follow-up)	yes (NPR)
Date of surgery	only IBD-related surgery; others might be in medical report	yes	yes (NPR)
Reduced mobility	no (might be in medical report)	no	yes (immobilization cannot be reliably captured in the Swedish registers; inpatient care due to UC [i.e., UC as main diagnostic listing] which will capture hospitalized patients in NPR; by proxies, e.g. major orthopedic surgery [pelvis/abdomen, hip or knee replacement; knee arthroscopy]; any surgery that requires immobilization post- procedure including fracture surgery and amputation of lower limbs; some types of vascular and orthopedic surgery)
Recent hospitalization (within 1 month prior to the index date or at any time during follow-up)	no (might be in medical report)	yes (hospitalizations are registered during follow-up)	yes (hospitalization record in the inpatient part of the NPR;

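### Table 5 marks recent hospitalization, a baseline VTE risk factor, as available in ICC, but the only ICC source it states covers follow-up and none is stated for the month before filgotinib start

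*Protocol*

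**What the plan says.** Protocol Section 8.3.1 includes recent hospitalization in the list of baseline characteristics and defines it as "hospitalization within 1 month prior to the index date or at any time during follow-up". Annex 3, Table 5 repeats the definition, "Recent hospitalization (within 1 month prior to the index date or at any time during follow-up", in the VTE part of the block headed "Variables assessed at baseline (start [index] date of filgotinib".

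The ICC cell of that row is "yes (hospitalizations are registered during follow-up". The next row, date of hospitalization, is a plain 'yes' for ICC. The SWIBREG cell cites the inpatient part of the National Patient Register. The ENEIDA cell is 'no', with the medical report as a possible source.

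Section 8.4.2.4.1 sets out what ICC records at Week 0. It names disease history items and then "location of previous IBD surgery, medical history, IBD medication history, and smoking status will be collected"; hospitalization is not mentioned. Section 8.4.2.4.2, on the follow-up visits, does mention it, under "complications (surgery, hospitalization".

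**The concern.** Section 7 makes prescribing in patients with VTE risk factors a named part of the adherence objective. What matters for that objective is the patient's risk when filgotinib was started. An admission in the preceding month bears on it; an admission some months into treatment does not.

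Reduced mobility is marked 'no' for ICC in Table 5, so hospitalization is the natural remaining proxy for immobilization there, and its pre-index part has no stated source. Section 8.7 also plans to describe the maintenance dose in patients at high risk of VTE. If this item counts towards that subgroup, its ICC membership would be partly decided by events after the start of treatment.

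The 'yes' has a practical consequence. Several ICC gaps shown as 'no' in Table 5 carry a note that the item can or will be added. This one is shown as available, so nothing prompts anyone to add it.

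**Working it through.** The point is about data capture, so the main check sets the entries side by side.

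1. **Window.** Section 8.3.1 and Table 5 agree: one month before index, or any time in follow-up. There are two parts, and only the first can describe status at the prescribing decision.
2. **Stated ICC source, follow-up part.** Table 5 and Section 8.4.2.4.2 both give one. The 'yes' is supported.
3. **Stated ICC source, pre-index part.** The Table 5 comment gives none, and the Week 0 list gives none beyond generic medical history.
4. **Neighbouring ICC rows.** For recent surgery the cell covers both sides of the index date: "history and location of IBD surgery is collected, and any IBD- surgery during follow-up". Previous VTE and clotting disorder are attributed to medical history or comorbidity. The hospitalization row has no such attribution.
5. **SWIBREG.** Inpatient register records exist before and after the index date, so both parts can be derived.

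**The plan's own figures.** No figure is given for recent hospitalization. The nearest is the precision example in Section 8.5 for a 10% risk proportion with n = 300: SE = √(0.10 × 0.90 / 300) = 1.73%, and 10% ± 1.96 × 1.73% = 6.6% to 13.4%. This reproduces the stated 1.7% and 6.6% to 13.4%. The example takes the item as measured; it does not address capture.

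**Illustrations.** The admission shares, capture shares, admission rates and follow-up times below are assumptions, not document figures.

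- *Patients at issue.* Section 8.9 gives 54 ICC patients between 12 November 2021 and 10 March 2023, which is 483 days. At a constant rate over four years (1,461 days), 54 / 483 × 1,461 ≈ 163 starters. If 5%, 10% or 20% were admitted in the month before start, that is about 8, 16 or 33 patients.
- *Pre-index part as recorded.* If a share s of patients has earlier ICC follow-up that captures such admissions, the recorded proportion is p × s.

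| True pre-index share p | s = 0 | s = 25% | s = 50% |
|---|---|---|---|
| 5% | 0% | 1.3% | 2.5% |
| 10% | 0% | 2.5% | 5.0% |
| 15% | 0% | 3.8% | 7.5% |

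- *Composite as recorded.* With an admission rate λ per year over t years, post-start admissions alone flag 1 − exp(−λt) of patients. With λ = 0.05 and t = 0.5 this is 2.5%; with λ = 0.20 and t = 2 it is 33%.

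The last two illustrations pull in opposite directions. The pre-index part is under-recorded, while the composite is filled by later admissions.

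**The case against.** The strongest reply is that the row defines a composite, and for that composite the ICC 'yes' is right for one half and its comment openly says which. That stands. A reader might infer that the 'yes' is simply wrong; it is wrong only if read as covering the month before start.

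A reader might also infer that the Dutch pre-index proportion must be zero by construction. The documents do not support that:

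- Under Sections 8.2.1.2 and 8.4.2.4, patients moving to filgotinib from another ICC-registered drug were already followed, so some earlier admissions may be on record.
- Week 0 collects medical history, and Section 8.4.2 says data are extracted from patient files. Section 8.4.2.4.1 may list content areas rather than every form field.
- Section 8.7 tabulates missing values and leaves them out of percentages, so an item coded as missing does not become 'no'.

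Each of these helps only in part. Registration stops when a drug is stopped, first-time ICC entrants have no earlier follow-up, and no one-month window is stated for medical history. The rule in Section 8.7 helps only if the pre-index part is actually coded as missing; a flag built from follow-up admissions would default to 'no'. The ICC rule in Section 8.7.1.2, which treats missing as nonresponse, has no meaning for a risk factor.

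A third tempting inference is that the Dutch VTE-risk proportion would look lower than the Swedish one. That is not shown. Post-start admissions raise the ICC figure, and in SWIBREG admissions with IBD as main diagnosis are to be treated as flares, so how they count in this row is unclear.

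It is also fair to say that hospitalization is not named in the protocol's summary of the SmPC's VTE risk factors (Section 6), that ICC does have recent surgery, previous VTE and clotting disorder, that no formal comparison between registries is planned, and that Section 8.9 warns in general terms that capture differs. These points limit the consequences. They do not supply a source for the missing month, and the SAP cannot analyse data that were not collected.

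**Conclusion.** The point holds in a limited form. Table 5 marks a baseline VTE risk factor as available in ICC, but the stated source supports only the follow-up half. Followed as written, the ICC value will rest mainly on admissions after treatment started. It cannot describe VTE risk at the prescribing decision and is not comparable with a SWIBREG value based on inpatient records for both windows.

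Neither the direction nor the size of the difference can be fixed from the document. The figures of about 163 starters and 8 to 33 patients rest on a constant enrolment rate and an assumed 5% to 20% admission share. They would overstate the loss if some admissions are captured elsewhere. The conclusion does not depend on them: it rests on the absence of any stated ICC source for the month before index, which is an inference from the item lists rather than something the protocol says outright. The change should be made, because it is cheap and concerns a named objective.

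**What to change.** - In Table 5, split the ICC cell into 'pre-index: no stated source; follow-up: yes'.
- Add one ICC Week 0 item, taken from the patient file: admission in the month before filgotinib start, yes or no, with date. Table 5 already says lipid measurements will be added in ICC, so the item can go into the same form update. Complete it from files for ICC patients who have already started.
- Report the pre-index and follow-up parts separately in every registry, and use only the pre-index part to describe risk at the prescribing decision.
- Where the pre-index part was not collected, report it as not available, never as 'no' or 0%.

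The cost is one extra eCRF item, a small file look-up for existing ICC patients, and a few words in Table 5 and the SAP.

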The chosen design of a prospective non-interventional registry-based follow-up study allows the investigation of the specific research questions of this DUS using the data collection infrastructure of 3 existing and established IBD registries based on real-world data (European Medicines Agency, 2021). In addition, the 3 data sources have been combined into 1 common

protocol to align the data collection process of this study as much as possible aiming for increased consistency in design (Klungel et al., 2016).

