#### Follow-up

Among women starting filgotinib, the number and proportion who become pregnant during follow-up will be reported. Similarly, the number and proportion of patients who have a new

diagnosis of TB during follow-up, a serious acute infection, a diagnosis of viral hepatitis, concomitant treatment with other immunosuppressants, or who are administered a live attenuated vaccine will be reported. In patients with TB, or a serious infection identified during follow-up, it will be assessed whether treatment was stopped or interrupted after the diagnosis. The proportion of patients who have a test for lipids at around 12 weeks since initiation of filgotinib will be reported.

Should a VTE event occur, subsequent changes to filgotinib use will be reported (filgotinib treatment persistence or discontinuation).

Assessment of the filgotinib maintenance dose during follow-up will also be done in the subgroup of patients at high risk of MACE, VTE, or malignancy. In addition, the average daily dose during the maintenance period and the duration of use during the follow-up period will be reported.

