#### none

Sec t	ion 6: Outcome definition and measurement	Yes	No	N/A	Section Number
6.1	Does the protocol specify the primary and secondary (if applicable) outcome(s) to be investigated?	$\boxtimes$			Section 7
6.2	Does the protocol describe how the outcomes are defined and measured?	$\boxtimes$			Annex 3 - Table 5
6.3	Does the protocol address the validity of outcome measurement? (e.g. precision, accuracy, sensitivity, specificity, positive predictive value, use of validation substudy)		$\boxtimes$		
6.4	Does the protocol describe specific outcomes relevant for Health Technology Assessment? (e.g. HRQoL, QALYs, DALYS, health care services utilisation, burden of disease or treatment, compliance, disease management)				

Comments:

none			

Sect	ion 7: Bias	Yes	No	N/A	Section Number
7.1	Does the protocol address ways to measure confounding? (e.g. confounding by indication)			$\boxtimes$	
7.2	Does the protocol address selection bias? (e.g. healthy user/adherer bias)	$\boxtimes$			Section 8.9
7.3	Does the protocol address information bias? (e.g. misclassification of exposure and outcomes, time-related bias)	$\boxtimes$			Section 8.9
Comn	nents				

Sec t	tion 8: Effect measure modification	Yes	No	N/A	Section Number
8.1	Does the protocol address effect modifiers? (e.g. collection of data on known effect modifiers, subgroup analyses, anticipated direction of effect)			$\boxtimes$	
Comn	nents:				

				1	1
Sec	tion 9: Data sources	Yes	No	N/A	Section Number
9.1	Does the protocol describe the data source(s) used in the study for the ascertainment of:				
	9.1.1 Exposure? (e.g. pharmacy dispensing, general practice prescribing, claims data, self-report, face-to-face interview)	$\boxtimes$			Section 8.4
	9.1.2 Outcomes? (e.g. clinical records, laboratory markers or values, claims data, self-report, patient interview including scales and questionnaires, vital statistics)				Section 8.4
	9.1.3 Covariates and other characteristics?				Section 8.4 & Annex 3 - Table 5
9.2	Does the protocol describe the information available from the data source(s) on:				
	9.2.1 Exposure? (e.g. date of dispensing, drug quantity, dose, number of days of supply prescription, daily dosage, prescriber)	$\boxtimes$			Annex 3 - Table 5
	9.2.2 Outcomes? (e.g. date of occurrence, multiple event, severity measures related to event)			$\boxtimes$	

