Variable	Availability in individual registries yes/no (additional comments)		
	ENEIDA (ES)	ICC (NL)	SWIBREG (SE)
			hospitalizations with IBD as the main diagnostic listing will be treated as flares)
Date of hospitalization	no (might be in medical report)	yes	yes (NPR)
Hx of blood clotting disorder or blood clots	no (might be in medical report)	yes (as part of medical history/comorbidity)	yes (NPR)
Concomitant use of combined hormonal contraceptives	no (might be in medical report)	no (but can be added)	yes (NPR)
Concomitant use of hormone replacement therapy	no (might be in medical report)	no (but can be added)	yes (NPR)
SmPC section 4.6: Fertility, pregnancy and lactation			
Advice on contraception in women of childbearing potential	no	no	no
Breastfeeding	no (might be in medical report)	no (but can be added)	no
	Variables assessed during follo	w-up	
Filgotininb treatment status			
Discontinuation	yes	yes	yes (SWIBREG, PDR)
Date of discontinuation	yes	yes	yes (SWIBREG, PDR)
SmPC section 4.2: Posology (Maintenance treatment)			
Maintenance filgotinib dose (after a maximum of 22 weeks of induction treatment)	yes (if not available, might be in medical report)	yes	yes (PDR)
SmPC section 4.3: Contraindications			

Variable	Availabil (ad		ries
	ENEIDA (ES)	ICC (NL)	SWIBREG (SE)
Tuberculosis (TB)	yes (if not available, might be in medical report)	yes	yes (SmiNet)
Dx date TB	yes (if not available, might be in medical report)	yes	yes (SmiNet)
Serious infection (SI)	yes (if not available, might be in medical report; a proxy definition of infection severity can be used to align with the definition of the other registries, based on information available from an eCRF field on the outcome of the infection [such as death, hospital admission])	yes (infections that lead to hospitalization or intravenously administrated antibiotic or antiviral medication)	yes (ICD-10 codes as recorded in the NPR or the 'infectious disease register' [for tuberculosis] including overall codes for e.g. sepsis or septic shock or for specific infectious disease categories being the main or contributory diagnostic listing for a hospitalization)
Dx date SI	yes (if not available, might be in medical report)	yes	yes (NPR)
Pregnancy	yes (if not available, might be in medical report)	yes	yes (Medical Birth Register; could be retrieved following child birth)
Date of pregnancy	yes	yes	yes (Medical Birth Register; could be retrieved following child birth)

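### Table 5 identifies follow-up serious infection by three non-equivalent criteria, so part of any difference between registries would come from the rule; a common admission-based row would separate it

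*Protocol*

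**What the plan says.** Annex 3, Table 5, follow-up block on contraindications, row for serious infection, has three entries.

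- **ICC:** "infections that lead to hospitalization or intravenously administrated antibiotic or antiviral medication".
- **SWIBREG:** ICD-10 codes from the National Patient Register (NPR), or from the infectious disease register for tuberculosis. They include overall codes such as sepsis, or "specific infectious disease categories being the main or contributory diagnostic listing for a hospitalization".
- **ENEIDA:** "a proxy definition of infection severity can be used to align with the definition of the other registries", drawn from "an eCRF field on the outcome of the infection [such as death, hospital admission" being the examples given.

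Annex 2, checklist item 6.2 ("Does the protocol describe how the outcomes are defined and measured") is answered yes and refers to Annex 3, Table 5.

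Section 8.7 (Follow-up) reports the number and proportion of patients with a serious acute infection. In patients with such an infection, "it will be assessed whether treatment was stopped or interrupted after the diagnosis". Section 8.1 says the three sources share one protocol "to align the data collection process of this study as much as possible aiming for increased consistency in design".

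**The concern.** ENEIDA is to be aligned with a definition that the other two registries are taken to share, and they do not share one. ICC has an intravenous-treatment limb that the SWIBREG entry lacks. SWIBREG admits contributory diagnoses, which do not show that the infection led to the admission, as ICC requires. ENEIDA names death, which neither of the others does.

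Active serious infection is a contraindication (Section 6), so what happens to filgotinib after one is an adherence result under objective b. The case definition sets the numerator of the reported proportion and the denominator of the stopping result. Each registry runs its own analysis, but the results meet in a consolidated report (Section 5), where countries will be compared. A difference produced by the rule could be read there as a difference in prescribing or in patients.

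**Working it through.** **1. The criteria side by side (Table 5).**

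| Situation | ICC | SWIBREG | ENEIDA |
|---|---|---|---|
| Infection leads to admission | case | case, if a listed code is recorded | case |
| Intravenous anti-infective, no admission | case | not a case, if the hospitalization wording governs every limb | not a case on the outcomes named |
| Admission for another reason, listed infection contributory only, no intravenous treatment | not a case | case | unclear |
| Fatal infection, no admission, no intravenous treatment | not a case as worded | not a case as worded | case |

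Only the first row can be shared by all three.

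**2. What each registry can supply.** Hospital admission is available in all three: ICC follow-up visits record hospitalization and infections (Section 8.4.2.4.2), the NPR covers inpatient care (Section 8.4.3.2), and the ENEIDA outcome field names admission. Death is named for ENEIDA and is feasible for SWIBREG through the Cause of Death Register (Section 8.4.3.6). For ICC, death ends follow-up (Section 8.2.4), but no field linking a death to an infection is described.

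**3. Scale of sampling error.** The protocol gives no figure for serious infection under any rule. Table 4 (Section 8.5) gives standard errors. With SE = √(p(1−p)/n) and n = 500:

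- p = 2%: 0.63 points (table 0.6)
- p = 5%: 0.97 points (table 1.0)
- p = 10%: 1.34 points (table 1.3)

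All 16 cells of Table 4 reproduce to rounding.

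**4. Illustrative shift in the proportion.** Assume a common-definition proportion p, and that one registry's wider limb adds a fraction a of further patients. The shift is p × a. Both p and a are assumptions. The last column is the standard error of a difference between two registries of 500 each, √(2p(1−p)/500).

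| p | Shift, a = 10% | Shift, a = 50% | SE, one registry | SE, difference |
|---|---|---|---|---|
| 2% | 0.2 | 1.0 | 0.6 | 0.9 |
| 5% | 0.5 | 2.5 | 1.0 | 1.4 |
| 10% | 1.0 | 5.0 | 1.3 | 1.9 |

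(percentage points)

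The shift runs from well below sampling error to well above it. Since 500 is a ceiling, smaller registries would have larger standard errors.

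**5. Illustrative effect on the stopping result.** At p = 5% and n = 500 the common definition gives 500 × 0.05 = 25 patients. The wider limb adds 2.5 to 12.5, so added patients make up 2.5/27.5 = 9% to 12.5/37.5 = 33% of the denominator. If the proportion stopping is s₁ in common cases and s₂ in added cases, the reported value moves by (s₁ − s₂) × a/(1 + a), that is, by 9% to 33% of the gap between them. If the gap is nil, nothing moves.

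**6. A related mismatch.** For active serious infection at baseline, Table 5 names the Population Register and the Prescribed Drug Register as the SWIBREG sources. The follow-up row uses the NPR. Section 8.4.3.7 describes the Population Register as holding residency, migration and death information, not infection diagnoses.

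**The case against.** The best counter-argument is that Table 5 lists availability with comments, that the ENEIDA entry is optional and its outcomes are only examples, and that Section 8.7 sends detailed methods to a common, harmonized SAP, which is not at hand. The study is descriptive, no pooling or between-country test is stated, and Section 8.9 warns of heterogeneity between registries. It stands that the harm is limited to comparability and that the SAP may settle the rule. But checklist item 6.2 names Table 5 as the place of definition, the alignment target it cites does not exist, and Section 8.9 speaks only generally, without naming this variable or separating rule-made from real differences.

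A reader might infer more than the text supports:

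- **That all three registries could apply admission or death.** The death limb is not documented for ICC.
- **That any Swedish admission with an infection code counts,** such as a wound infection after colectomy. SWIBREG names specific categories, and whether that infection is among them is unknown. ENEIDA's handling is also unclear.
- **That outpatient intravenous treatment is certainly a case in ICC alone.** The NPR also covers non-primary outpatient visits, and it is ambiguous whether the hospitalization wording governs every SWIBREG limb.
- **That the Swedish figure would be inflated by a known factor.** No document gives the share of contributory-only cases. A share of admissions also does not carry over to patients, because a patient with both kinds of admission counts under either rule.
- **That contributory infections do not belong in the stopping denominator.** Sepsis acquired during an admission for colitis is still a serious infection. Making main diagnosis the only reported rule would discard such cases.

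**Conclusion.** The concern holds as one of comparability. Table 5 sets three criteria that are not equivalent, and ENEIDA's proxy points to a shared definition that does not exist. The same patient can be classified differently by country, which affects both the reported proportion and the stopping or interruption result.

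The size cannot be obtained from the documents. On the assumed ranges above it is 0.2 to 5.0 percentage points in the proportion, which may be smaller or larger than sampling error. No registry's own result is shown to be wrong under its own definition. The point deserves action because a shared admission limb is available in all three registries and costs little to report. An SAP that already fixes a common rule would leave only the Table 5 wording to correct.

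**What to change.** 1. Keep each registry's own definition and label it beside its result.
2. Add one common row in all three registries: infection leading to hospital admission. For SWIBREG, use infection as main diagnosis in NPR inpatient data, with main-or-contributory shown separately. For ICC, use the hospitalization limb only. For ENEIDA, use the outcome of hospital admission, which gives its proxy a defined target.
3. For the common row, report both the proportion and stopping or interruption after diagnosis.
4. Show intravenous-only and fatal infections as labelled registry-specific additions, since a death limb is not documented for ICC.
5. Reconcile the SWIBREG sources in the baseline row with those in the follow-up row.

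The cost is wording in Table 5 and the SAP, and one extra row per registry. The common count will be lower than under the wider definitions and will omit some infections arising in hospital. If the contributory-only share is large, the Swedish reduction could be substantial. Those cases stay visible in the registry-specific row, which is why it should be kept.
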